7.2. Secondary Efficacy Endpoints

Disease Control Rate

Disease control is achieved by subjects who exhibit a BOR of CR, PR, or SD according to RECIST v1.1. DCR is defined as the number of subjects who exhibit a BOR response of CR, PR, or SD divided by the number of subjects evaluable for analysis and will not be summarized or reported in the CSR synopsis.

Progression Free Survival

PFS is defined as the number of weeks from the date of first dose of study treatment to the first date of objectively determined progressive disease according to RECIST v1.1 or death from any cause and is computed as described in Section 5.3. The primary analysis of PFS will include tumor assessments collected after the end of study treatment. Tumor assessments taken after switch to another anti-cancer therapy will be excluded from consideration.

The first date of objectively determined progressive disease would be the earliest date of any post-baseline overall response finding of progressive disease as part of the tumor lesion assessment data or death, unless a subject is censored at an earlier date. If an assessment occurs over several days, the method described in Section 5.6 will be used. If there are no adequate assessments for a subject, they will be censored on their first dose date unless they died prior to having their first assessment (in which case they will be considered to have had a PFS event of death). If a subject receives subsequent anticancer therapy prior to documentation of progressive disease, PFS will be censored at the latest adequate assessment prior to therapy initiation.

Subjects who progress or die following an extended period of follow up will also be censored at a latest adequate assessment prior to the end of a predefined lapse window, even if information is available regarding progression or death after this extended period. Should a subject die after the end of this lapse window they will be censored at their first dose date. The lapse window after which PFS events will not be considered is defined in Section 5.7.

Otherwise, if a subject does not have documented progression, the subject will be censored at the latest adequate assessment.

PFS will be listed.

Sponsor: Aduro Biotech, Inc.
Protocol Number: ADU-CL-14
Version and Date: Version 1.0, 13Mar2018

Overall Survival

OS is defined as the number of weeks from the date of first dose of study treatment to the date of death from any cause and is computed as described in Section 5.3. Subjects still alive as of the data cut-off date will be censored on the last known alive date from mortality status follow up. For subjects that are lost to follow up, the last visit in the database or last contact date where the subject is documented to be alive will be used to estimate last known date alive.

OS will be listed.

Duration of Response

DOR will be computed for subjects who have been identified as a responder (achieved an overall response of CR or PR according to RECIST v1.1 during the PFS observation period); it will be computed as described in Section 5.3, where the reference date will be the first date where a subject has been documented to have achieved a responder designation. Censoring algorithms similar to those identified for PFS will be used for DOR.

DOR will be listed.

7.3. Additional Efficacy Endpoints and Analyses

Efficacy endpoints ORR, DCR, DOR and PFS defined according to irRECIST will not be derived.

8. PHARMACOKINETICS/PHARMACODYNAMICS

NA

9. QUALITY OF LIFE

NA

10. SAFETY

All safety analysis reporting will be based on the SAF.

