6.2.3 Dosing Eligibility and Delayed Dosing

Subjects must have adequate organ function confirmed (as defined by the laboratory values in Table 6-1) prior to each dosing cycle where CRS-207 is administered; laboratory tests may be performed up to 3 days before dosing.

Table 6-1 Dosing-Eligibility Requirements

Hematologic	Renal	Hepatic
WBC \geq 3000/ μ L	Creatinine \leq 1.5 \times ULN	AST/ALT \leq 5 \times ULN
ANC \geq 1000/ μ L		Bilirubin \leq 1.5 \times ULN OR \leq 3 \times ULN if due to Gilbert's disease
Platelets \geq 90,000/ μ L		
Hemoglobin \geq 8 g/dL		

ALT = alanine aminotransferase; ANC = absolute neutrophil count; AST = aspartate aminotransferase; ULN = institutional upper limit of normal; WBC = white blood cell

Subjects who do not meet dosing eligibility requirements will be monitored; dosing may be delayed up to 2 weeks, after which time it will be considered missed and the subject would continue onto the next scheduled dose. If a dose is delayed more than 2 weeks, contact the Medical Monitor for further instruction on continued dosing.

Pembrolizumab may be administered up to 3 days before or after the scheduled Day 1 of each cycle due to administrative reasons. If subjects on same-day dosing schedule experience severe infusion-related reactions related to the pembrolizumab infusion, the CRS-207 infusion may be delayed to Day 2. CRS-207 must be administered one day after pembrolizumab administration. If the subject experiences a new AE or is recovering from an AE, CRS-207 administration may be delayed up to 7 days and the Sponsor must be notified. If a dose of CRS-207 is delayed beyond 7 days of pembrolizumab, the dose of CRS-207 should be withheld until the next cycle.

Dosing interruptions are permitted in the case of medical / surgical events or logistical reasons not related to study therapy (e.g. elective surgery, unrelated medical events, vacation, and/or holidays). Subjects should be placed back on study therapy within 3 weeks of the scheduled interruption, unless otherwise discussed with the Sponsor. The reason for interruption should be documented in the Subject's study record.

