6.5.4 Analysis Sets

Evaluable Analysis Set (EAS) is defined as all subjects who received at least 1 dose of CRS-207 and have at least one evaluable post-baseline RECIST tumor response assessment or were discontinued due to toxicity. The EAS will be the primary population for analyses of tumor-related endpoints (ORR, DCR, DOR, and PFS).

Full Analysis Set (FAS) is defined as all subjects who received at least 1 dose of CRS-207. The FAS will be used for analyses of OS, immunogenicity and other biomarker data, and sensitivity analysis of select tumor-related endpoints.

Safety Set (SAF) includes all subjects who received any study treatment (pembrolizumab or CRS-207). The SAF will be used for all analyses of safety data and may be used for select biomarker data.

Additional analysis sets (e.g. per protocol set) may be defined in the SAP.

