6. STUDY SUBJECT DATA

6.1. Analysis Sets

The Safety Analysis Set (SAF) includes all subjects who received any study treatment. All analyses of safety data will be conducted using the safety set. The SAF is the only analysis set used for all listings and analysis.

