6.8. Study Drug Exposure

Duration of treatment (in months, as described in 5.3) will be summarized as a continuous variable for CRS-207 and pembrolizumab separately.

The number of infusions of CRS-207 will also be reported as both a continuous and categorical outcome; categories for reporting will be < 5 infusions; 5 to 10 infusions; > 10 to 15 infusions; and > 15 infusions.

The number of cycles of administration (of any dose amount) of pembrolizumab will be reported as a continuous and categorical outcome; categories for reporting will include: < 5 Cycles; 5 to 15 Cycles; > 15 to 25 Cycles; and > 25 Cycles.

The average volume administered for each infusion (or cycle) will be summarized by therapy. This will be calculated for each subject in (mL / infusion or mL / Cycle):
(Sum of Total Volume Administered [mL]) / (Total Number of Administrations)

The average dose intensity for each pembrolizumab cycle will be summarized. This will be calculated for each subject in (mg / Cycle):
(Sum of Total Dose Received [mg]) / (Total Number of Administrations)

The incidence of infusion interruptions and dose reductions, as well as the total number of interruptions and dose reductions, will be displayed by therapy. Reasons for infusion interruptions will be summarized by therapy.

The exposure summary display will be based on the Safety Set.

CRS-207 and pembrolizumab administration, infusion interruption, and dose reduction information, as well as derived drug exposure metrics, will be listed.

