10.1. Adverse Events

AEs will be recorded from the time of first study drug administration until 28 days after the last dose of study drug or until a subject initiates a new cancer therapy, whichever is earlier. AEs will also be assessed for severity using the NCI-CTCAE v. 4.03, relationship to each therapy (Definitely Related, Probably Related, Possibly Related, Unlikely Related, Not Related), and seriousness (Yes, No). AEs will be considered treatment-emergent if their onset occurs within the on-therapy period. Summary of events related to any study treatment will be provided.

Sponsor: Aduro Biotech, Inc.
Protocol Number: ADU-CL-14
Version and Date: Version 1.0, 13Mar2018

An overview of treatment-emergent AEs (TEAEs) will be produced, including counts and percentages of subjects with any incidences of: TEAEs, CTCAE Grade 3 or higher TEAEs, TEAEs related to study treatment, CTCAE Grade 3 or higher TEAEs related to study treatment, serious adverse events (SAEs), TEAEs leading to study drug discontinuation, infusion-related reactions (IRRs), and fatal TEAEs.

A separate overview of AEs identified as IRRs related to CRS-207 will be provided. This display will include the number of infusions received by subjects, the number of subjects having an IRR, total number of IRRs per subject, maximum IRR grade, and dose modifications resulting from IRRs.

Adverse events will be coded based on the Medical Dictionary for Regulatory Affairs (MedDRA) for reporting by system organ class (SOC) and preferred term (PT) in descending order of overall incidence. For these summaries, subjects with multiple AEs with the same SOC and/or PT will only be counted once at each level of summarization.

Summaries of adverse events by SOC and PT will include the following types:

- TEAEs;
- TEAEs related to any study treatment (Definitely Related, Probably Related, or Possibly Related);
- CTCAE Grade 3 or higher TEAEs;
- CTCAE Grade 3 or higher TEAEs related to any study treatment;
- CRS-207 infusion-related reactions;
- SAEs.

To account for potential differences in the extent of exposure between the treatment categories, a subject-year adjusted rate will also be presented. The rate is calculated as the number of subjects with an event divided by the total subject-years of safety observation, where subject-years of safety observation for each subject is defined as duration of safety observation (defined in Section 5.3) in days divided by 365.25.

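### The CRS-207 infusion-reaction percentages use a denominator that can include subjects never given CRS-207: a minor point that matters only if such subjects exist

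*SAP*

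**What the plan says.** SAP 6.1 sets the population: "The Safety Analysis Set (SAF) includes all subjects who received any study treatment". It adds: "The SAF is the only analysis set used for all listings and analysis". Section 10 repeats the rule for safety: "All safety analysis reporting will be based on the SAF". For dosing, SAP 6.8 says: "The exposure summary display will be based on the Safety Set". The titles of Tables 14.1.4 (exposure), 14.3.1.2.1 (CRS-207 infusion reactions) and 14.3.1.2.2 (infusion reactions by system organ class and preferred term) all name the Safety Analysis Set.

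Two of these displays are specific to one drug. SAP 10.1 promises: "A separate overview of AEs identified as IRRs related to CRS-207 will be provided". SAP 6.8 reports the number of CRS-207 infusions as a continuous variable and in categories, of which the lowest is fewer than 5. There is no category for 0.

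Protocol 6.5.4 separates the two kinds of treated subject. Its Safety Set accepts either drug. By contrast, "Full Analysis Set (FAS) is defined as all subjects who received at least 1 dose of CRS-207". The SAP does not carry the FAS forward.

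**The concern.** A subject who never received CRS-207 cannot have a CRS-207 infusion reaction. If that subject is in the denominator, the percentage no longer describes people exposed to the drug, and the error can only lower it. The same subject adds a zero to the count of reactions per subject. In the categorical exposure summary the subject is merged with those who had 1 to 4 infusions.

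The SAP lists efficacy without summarizing it (SAP 7 and 11), so the safety tables carry most of the summarized results. It is worth having the denominator of a drug-specific rate right.

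**Working it through.** The documents state no infusion-reaction rate and no count of subjects without CRS-207, so there is no planned figure to reproduce. The check has two parts.

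**Can a subject enter the SAF without CRS-207?** The SAF needs one dose of either drug. In Cycle 1 the drugs are given on consecutive days, pembrolizumab first (Protocol 6.1, SAP 3.1). Protocol Table 6-5 ends further study drug treatment permanently after a Grade 3 or 4 pembrolizumab infusion reaction. If that happens on Cycle 1 Day 1 and is applied to both drugs, the subject is in the SAF with zero CRS-207 infusions. Protocol 6.2.4 also allows single-agent continuation with Medical Monitor approval, so the outcome is possible rather than certain. Withdrawal of consent between the two days would have the same effect. The definition therefore admits such subjects.

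**Does any other rule remove them from the percentage?** SAP section 4 bases percentages on nonmissing values. A subject with no recorded reaction is a non-reactor, not a missing value, so the subject stays in the denominator.

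**Size.** Let N be the SAF size, k the number never given CRS-207, and x the number with a CRS-207 reaction.

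- Rate in exposed subjects: x/(N − k)
- Rate as printed on the SAF: x/N
- Ratio of printed to exposed: (N − k)/N

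The only N in the documents is the planned figure of about 79. The study was closed early (SAP 3.5), so smaller values are shown as well. All values of k, and the 60% rate in exposed subjects, are assumptions for illustration.

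| N | k | (N − k)/N | A 60.0% rate prints as |
|---|---|---|---|
| any | 0 | 1.000 | 60.0% |
| 79 | 1 | 0.987 | 59.2% |
| 79 | 3 | 0.962 | 57.7% |
| 79 | 8 | 0.899 | 53.9% |
| 40 | 1 | 0.975 | 58.5% |
| 20 | 1 | 0.950 | 57.0% |
| 20 | 2 | 0.900 | 54.0% |
| 12 | 1 | 0.917 | 55.0% |
| 12 | 2 | 0.833 | 50.0% |

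The relative loss per unexposed subject is 1/N: 1/79 = 1.3%, 1/20 = 5%, 1/12 = 8.3%.

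**The case against.** The strongest reply is that the SAP does what the protocol told it to do. Protocol 6.5.4 assigns the SAF to all analyses of safety data. It gives the FAS to overall survival, biomarkers and sensitivity analyses of tumor endpoints. A reader might infer that the SAP removed a CRS-207-exposed safety denominator, but none was ever planned. This part of the reply stands. It explains how the denominator arose, but it does not make it suitable for a reaction to one drug.

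A reader might also infer that the rate is in fact diluted. The documents do not support that. Neither reports a single pembrolizumab-only subject, and with k = 0 the SAF and FAS coincide.

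Nor do the delay rules in Protocol 6.2.3 establish permanent non-exposure. When CRS-207 is delayed more than 7 days after pembrolizumab, "the dose of CRS-207 should be withheld until the next cycle". That is deferral, and a subject dosed in Cycle 2 is exposed. Failing Table 6-1 in Cycle 1 is also a weak route, because the entry limits are mostly as strict or stricter (neutrophils 1500 against 1000, platelets 100,000 against 90,000, hemoglobin 9 against 8).

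Finally, non-exposure is partly visible already. The CRS-207 reaction overview shows infusions received, the continuous infusion summary prints n and a minimum, and Listing 16.2.5.1 gives administration by subject. So it would be too strong to say that the plan hides non-exposure. Only the category label does so, and a reader would still have to rebuild the reaction percentage by hand.

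**Conclusion.** The point holds in a limited, conditional form. The stated population rule admits subjects never given CRS-207 into the denominator of CRS-207 reaction percentages, and no other rule takes them out. Any bias is downward by the factor (N − k)/N. It is slight at the planned size unless several such subjects exist, and it becomes noticeable only if early closure left a small treated group. The true N and k cannot be found from the documents. The plan has no comparator, no significance test and no decision rule that uses this percentage. Severity is minor.

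**What to change.** - **SAP 10.1, Table 14.3.1.2.1:** use subjects with at least one CRS-207 dose as the denominator for CRS-207 infusion-reaction percentages. The protocol's FAS already defines this group.
- **Table 14.3.1.2.2:** do the same to the extent that it reports CRS-207 reactions. Its title does not name the drug, although the list of summaries in SAP 10.1 does. Any pembrolizumab reactions shown there stay on the SAF.
- **Table 14.1.4:** keep the SAF, but split the fewer-than-5 category into 0 and 1 to 4. The number never given CRS-207 is then printed. Restricting this table to exposed subjects would leave the 0 row empty by definition.
- **All other safety tables:** keep the SAF.
- **SAP 6.1, 10 and 11:** add the exception to the single-set statements, and record it as a change, since the protocol assigned the SAF to all safety analyses.

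The cost is one population flag and a second denominator to footnote. Every subject had completed the end-of-treatment visit by 31 January 2018 and the SAP is dated 13 March 2018, so k can be counted directly from the administration data. If it is zero, no reaction percentage changes.

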10.1. Adverse Events

AEs will be recorded from the time of first study drug administration until 28 days after the last dose of study drug or until a subject initiates a new cancer therapy, whichever is earlier. AEs will also be assessed for severity using the NCI-CTCAE v. 4.03, relationship to each therapy (Definitely Related, Probably Related, Possibly Related, Unlikely Related, Not Related), and seriousness (Yes, No). AEs will be considered treatment-emergent if their onset occurs within the on-therapy period. Summary of events related to any study treatment will be provided.

Sponsor: Aduro Biotech, Inc.
Protocol Number: ADU-CL-14
Version and Date: Version 1.0, 13Mar2018

An overview of treatment-emergent AEs (TEAEs) will be produced, including counts and percentages of subjects with any incidences of: TEAEs, CTCAE Grade 3 or higher TEAEs, TEAEs related to study treatment, CTCAE Grade 3 or higher TEAEs related to study treatment, serious adverse events (SAEs), TEAEs leading to study drug discontinuation, infusion-related reactions (IRRs), and fatal TEAEs.

A separate overview of AEs identified as IRRs related to CRS-207 will be provided. This display will include the number of infusions received by subjects, the number of subjects having an IRR, total number of IRRs per subject, maximum IRR grade, and dose modifications resulting from IRRs.

Adverse events will be coded based on the Medical Dictionary for Regulatory Affairs (MedDRA) for reporting by system organ class (SOC) and preferred term (PT) in descending order of overall incidence. For these summaries, subjects with multiple AEs with the same SOC and/or PT will only be counted once at each level of summarization.

Summaries of adverse events by SOC and PT will include the following types:

- TEAEs;
- TEAEs related to any study treatment (Definitely Related, Probably Related, or Possibly Related);
- CTCAE Grade 3 or higher TEAEs;
- CTCAE Grade 3 or higher TEAEs related to any study treatment;
- CRS-207 infusion-related reactions;
- SAEs.

To account for potential differences in the extent of exposure between the treatment categories, a subject-year adjusted rate will also be presented. The rate is calculated as the number of subjects with an event divided by the total subject-years of safety observation, where subject-years of safety observation for each subject is defined as duration of safety observation (defined in Section 5.3) in days divided by 365.25.

A comprehensive listing of all AEs will be provided in a by-subject data listing, this will include information on:

- SAEs;
- TEAEs leading to treatment discontinuation; and
- Fatal AEs (with identification of those which occur within the on-therapy period).

Unacceptable Toxicities

Subjects will be monitored for unacceptable toxicities during the Safety Run-in Period [the first 28 days (through 7 days after the Cycle 2 dose)]. Unacceptable toxicities will be presented in the AE data listing.

Sponsor: Aduro Biotech, Inc.
Protocol Number: ADU-CL-14
Version and Date: Version 1.0, 13Mar2018

Deaths

The number and percent of subjects who died along with primary cause of death will be summarized overall (including the post-study survival surveillance period) and within 28 days of last dose of study drug. All death data will be listed.

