6.4.3.4 Adverse Events

AEs will be recorded from the time of first study drug administration until 28 days following the last dose of study drug or initiation of subsequent cancer-related therapy, whichever occurs first. SAEs should be reported per the timeframe and procedures described in [Section 7.3](#). If the EOT visit occurs less than 28 days from the last dose of study drug, the subject will be contacted by telephone 28 days (+ 3 days) after the date of last study drug administration to complete the AE reporting period. A follow-up contact for AEs will also be conducted 1 day after each CRS-207 infusion (and one day after pembrolizumab infusions beyond Cycle 5 where CRS-207 is not administered). Contact must be documented in the study records.

All AEs and abnormal clinical laboratory assessments will be assessed for severity using the NCI-CTCAE v. 4.03. The determination, evaluation, reporting, and follow-up of AEs will be performed as outlined in [Section 7](#).

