7 ADVERSE EVENT REPORTING AND FOLLOW UP

7.1 Adverse Events

An AE is defined as any untoward medical occurrence associated with the use of a drug in humans, whether or not considered drug related. An AE can therefore be any unfavorable and/or unintended sign (including an abnormal laboratory finding), symptom, or disease temporally associated with the use of an investigational medicinal product, whether or not related to the investigational medicinal product. All AEs, including observed or volunteered problems, complaints, or symptoms, are to be recorded on the appropriate eCRF.

AEs occurring from the time of first study drug administration and up to 28 days after the last dose of study drug or until a subject initiates a new cancer therapy, whichever is earlier, will be monitored and documented on the AE eCRF. AEs include clinical laboratory test variables and events observed by the Investigator; subjects should be instructed to report any AE that they experience to the Investigator. At each indicated visit, Investigators should make an assessment for AEs and record the event on the appropriate AE eCRF.

Wherever possible, a specific disease or syndrome rather than individual associated signs and symptoms should be identified by the Investigator and recorded on the eCRF. However, if an observed or reported sign or symptom is not considered a component of a specific disease or syndrome by the Investigator, it should be recorded as a separate AE on the eCRF. Additionally, the condition that led to a medical or surgical procedure (e.g. surgery, endoscopy, tooth extraction, or transfusion) should be recorded as an AE, not the procedure.

Any medical condition already present prior to the first dose of study drug should be reported in medical history unless the medical condition or signs or symptoms present at baseline change in severity or seriousness at any time during the study. In this case, it should be reported as an AE.

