7.3 Serious Adverse Event Reporting – Procedures for Investigators

7.3.1 Initial Reports

SAEs will be collected from the time of first study drug administration through 90 days following cessation of treatment, or 28 days following cessation of treatment if the subject initiates new anticancer therapy, whichever is earlier. SAEs and events of clinical interest must be reported to the Sponsor (or designee) within 24 hours of the knowledge of the occurrence. Outside of the 90-day period, only SAEs considered related to the administration of study drug must be reported to the Sponsor.

In the event an SAE is observed or reported, the SAE report will be completed as thoroughly as possible including all available details about the event and the signature of the Investigator. If the Investigator does not have all information about an SAE, the Investigator will not wait to receive additional information before notifying the Sponsor of the event and completing the form. The form will be updated when additional information is received.

Complete the paper SAE form for each SAE. The SAE form will be faxed or emailed to the Sponsor or designee within 24 hours of awareness of the initial or any follow-up information, and designated study personnel will be notified electronically. If the SAE falls on a weekend or

holiday, an email notification is acceptable but must be followed by an SAE reporting form on the next business day.

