5.4. Study Time Periods

Safety reporting will be classified by the following study periods for analysis:

Pre-therapy is defined as the period prior to a subject's first dose of study treatment.

On-therapy is defined as the period between first dose of study treatment and within 28 days following the last dose of study treatment.

Post-therapy is defined as the period of time following the on-therapy period.

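### AE recording stops at a new anticancer therapy, but SAE collection, the treatment-emergent window and the observation time run on to last dose + 28 days, so after an early switch only serious events can enter the TEAE counts

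*SAP*

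**What the plan says.** Four definitions bear on the weeks after the last dose.

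- **AE recording.** SAP 10.1 runs it to 28 days after the last dose "or until a subject initiates a new cancer therapy, whichever is earlier". Protocol 6.4.3.4 agrees ("until 28 days following the last dose of study drug or initiation of subsequent cancer-related therapy, whichever occurs first"), as does Protocol 7.1 for the AE eCRF.
- **SAE collection.** Protocol 6.4.3.4 takes SAEs out of that window ("SAEs should be reported per the timeframe and procedures described in" Section 7.3). Protocol 7.3.1 then collects them "through 90 days following cessation of treatment, or 28 days following cessation of treatment if the subject initiates new anticancer therapy, whichever is earlier".
- **Treatment-emergent window.** SAP 10.1 makes an AE treatment-emergent if its onset is on-therapy. SAP 5.4 says: "On-therapy is defined as the period between first dose of study treatment and within 28 days following the last dose of study treatment". Neither section mentions subsequent therapy.
- **Observation time.** SAP 5.3 defines the safety observation period as last treatment date + 28 days, minus first dose date, + 1. SAP 10.1 uses it as the denominator of the subject-year rates. It has no cut at new therapy either.

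A switch inside the 28 days is foreseen: Protocol 6.1 and 6.4 and SAP 3.1 say what to do with the EOT assessments when it happens. For efficacy, SAP 7.2 disregards tumor assessments made after a switch. SAP 10 has no matching rule.

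**The concern.** For a subject who switches early, the plan's windows disagree on the days between the switch and day 28. On those days a serious event can be collected and meets the TEAE definition. A non-serious event on the same day is not recorded. Whether an event is counted then depends on its seriousness, not only on its timing, and the ratio of serious to all events shifts. The subject-year rates are affected from the other side, because their denominator includes days on which most event types could not be captured.

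Safety carries most of the reporting here. SAP 7 and 11 list efficacy without summarizing it. Apart from disposition, baseline and exposure, every planned table in SAP 13.1 is a safety table. The exposed displays are the all-cause ones: the TEAE overview (14.3.1.1.1), TEAEs by SOC and PT (14.3.1.1.2), Grade 3 or higher TEAEs (14.3.1.1.4) and serious TEAEs (14.3.2.1). The tables of related events are partly protected by the investigator's attribution.

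**Working it through.** The plan states no figure on this point, so there is nothing to reproduce. The check compares the windows and then sizes the gap.

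**1. The windows.** Let new therapy start d days after the last dose, with d < 28.

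- AE recording ends at min(28, d) = d.
- SAE collection ends at min(90, 28) = 28.
- The treatment-emergent window and the observation time end at 28.

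The interval that is treatment-emergent but has only SAEs collected is 28 − d days:

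| d | SAE-only days |
|---|---|
| 7 | 21 |
| 14 | 14 |
| 21 | 7 |
| 27 | 1 |
| 28 or more | 0 |

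Subjects who do not switch within 28 days are unaffected. SAEs after day 28 are collected in some subjects but are not TEAEs.

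**2. The denominator.** Days counted under SAP 5.3 = treatment days + 28. Days with non-serious AEs recorded = treatment days + d, counting the day of the switch as recorded. The nominal 3-week cycle puts Cycle 2 Day 1 at Day 22 and Cycle 4 Day 1 at Day 64.

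- Last dose Day 22, d = 14: 22 + 28 = 50 counted and 22 + 14 = 36 recorded. 50/36 − 1 = 39% overstatement for that subject.
- Last dose Day 64, d = 14: 64 + 28 = 92 counted and 64 + 14 = 78 recorded. 92/78 − 1 = 18%.

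If a share f of subjects switches at d = 14, with all else equal, the subject-year rate for non-serious events is multiplied by 1 − 14f/(treatment days + 28):

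| f (assumed) | Last dose Day 22 | Last dose Day 64 |
|---|---|---|
| 10% | 0.97 | 0.98 |
| 30% | 0.92 | 0.95 |
| 50% | 0.86 | 0.92 |

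**3. The serious row.** The documents give no times to subsequent therapy and no SAE risk on it, so all three inputs are assumptions: 15–30% of subjects switch inside 28 days, and the SAE risk after the switch is 10–20% per 30 days. Mean overlap is 14 days if switches are spread evenly over days 0–28. The synopsis and SAP 3.1 place a 7-day antibiotic course before any subsequent cancer therapy. If that course has to be finished first, and switches are spread evenly over days 7–28, mean overlap is (28 − 7)/2 = 10.5 days.

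Share of subjects = share switching × (overlap/30) × risk.

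- Low: 0.15 × (10.5/30) × 0.10 = 0.00525, about 0.5 percentage points.
- High: 0.30 × (14/30) × 0.20 = 0.028, or 2.8 percentage points.

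These are upper values for the inputs used. They assume that every post-switch SAE reaches the dataset and belongs to a subject with no earlier SAE. A subject already counted in a row adds nothing to it. The range is in percentage points because the planned 79 is not a safe base: SAP 3.5 records that development stopped in December 2017, and the number treated is not stated.

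**The case against.** **Post-switch SAEs may never reach the tables.** Read alone, SAP 10.1 stops recording all AEs at the switch and treats seriousness as an attribute of those AEs. Protocol 7.3.1 uses a paper SAE form, and nothing says how it feeds the analysis dataset. This stands in part, so the claim has to be that such events may be counted. The SAP does point towards inclusion. Its AE listing is to identify which fatal AEs fall on-therapy, yet general AE recording never runs past last dose + 28 days. That flag has something to separate only if events from the longer SAE window are in the AE data.

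**A reader might infer that the next therapy's toxicity is being reported as toxicity of CRS-207/pembrolizumab.** The documents do not support that. An SAE soon after the last dose may come from the cancer (Protocol 7.1.1.1) or be a delayed immune-related event, which Protocol 6.3.5.2 says can appear months after the last pembrolizumab dose. Onset after the switch does not show cause.

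**A fixed last-dose-plus-28-days window is a conservative choice.** It would be if all AEs were collected to day 28. Here only serious ones are, so the question goes beyond preference: the analysis window does not match the plan's own recording rule.

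**The events can be traced and little depends on them.** Both are true. Dates in Listings 16.2.7.1 and 16.2.12 can be compared by hand, and this is an abbreviated plan for a synopsis of a closed single-arm study without significance tests. That limits the importance, but it does not make the tabulated counts and rates consistent.

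**Conclusion.** The mismatch is in the text and holds in a limited form. It concerns only subjects who start new anticancer therapy within 28 days of the last dose, and only onsets between that start and day 28. In those days SAEs may enter the all-cause TEAE rows while non-serious events cannot, and the days still count as observation time.

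The effect on the serious row is about 0.5 to 2.8 percentage points at most under the assumed inputs. It is smaller where subjects already had an SAE, and zero if post-switch SAEs are not loaded. The denominator gap does not depend on how SAEs are loaded. It can be large for one subject (39% in the Day 22 example) but is diluted across the cohort. This is a modest inconsistency, worth correcting because the correction is cheap. It is not evidence that the safety tables are materially wrong.

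**What to change.** For the TEAE tables and subject-year rates, end both the treatment-emergent window (SAP 5.4 and 10.1) and the safety observation period (SAP 5.3) at the earlier of last dose + 28 days and the day before new anticancer therapy starts. Take the start date from the subsequent-therapy data behind Listing 16.2.12. Show SAEs with onset after the switch, including those assessed as related, in a separate row or listing flagged as onset after new anticancer therapy, outside the main TEAE counts. Adding only the related ones back would not work: after the switch only serious events exist to be added, so inclusion would again depend on seriousness.

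Two details belong in the same edit. SAP 10.1 should say whether SAEs reported under Protocol 7.3.1 are loaded into the AE dataset. The partial-date rules for subsequent therapy in SAP 5.6 were written for efficacy, so an imputed start should not be allowed to fall before the last dose when it is used to cut the safety window.

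The cost is a few lines of SAP wording, one date comparison and one extra display. No new data are needed. All subjects had completed their EOT visit by the date of the SAP and unrecorded non-serious events cannot be recovered, so the change belongs in the analysis definitions. The downside is that a few late SAEs, including delayed study-drug events, move from the main tables to the flagged display. The separate summary of deaths within 28 days of last dose is unaffected.
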